## **Project Summary**

The aim of this Pilot study is to determine whether robotically targeted lower-limb pedaling therapy can increase the extent of stroke recovery on behavioral measures and induce brain plasticity as measured by functional magnetic resonance imaging (fMRI). Forty (40) adult stroke patients and 80 healthy controls will be enrolled in this study. Of the 40 patients, half will be randomly assigned to the robotically-targeted training ("robotic") group and will receive training on the targeted training task. The other half of the patients will perform a duration-matched aerobic pedaling exercise ("control" group). All stroke patients will be scanned before and after their training program while performing or imagining simple motor tasks. Behavioral assessments of motor and cognitive capacities will be collected at each timepoint. Healthy control subjects enrolled for device testing (20) will receive up to 5 training sessions in a modified robotic paradigm and 1 fMRI scan, in order to investigate motor learning and brain activity in a novel motor control task. Additional healthy pilot subjects (up to 60) will test training protocols and assessments during preparatory design phases of the project.

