### ***Functional MRI scans:***

- Participants who will undergo an MRI scan will be screened for MRI eligibility using the UW Department of Radiology's standard clinical MRI screening form.
- All patients in the study will be scanned at two time points (before and after intervention).
- Healthy Normals in the Typical Comparison group will be scanned once.
- Healthy Normals in the Pilot group will not be scanned.

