## **Robotic Training Group (Robotic Group): Procedure**

### ***Robotic therapy protocol description:***

The "Robotic" group will be trained using a robotic training protocol, designed to incentivize recovery of volitional motor control by dynamically changing task demands throughout the training period. One or more target tasks will be chosen to incentivize motor activity mimicking different sub-functions of gait, including some which are not normally excited in typical cycling behavior. Candidate tasks include: leg swing-through (hip flexion with knee extension near the most proximal pedal position); leg retraction (hip extension with knee flexion near the distal pedal position); leg extension (hip and knee extension – the power stroke of normal pedaling); leg retraction (hip and knee

flexion –the passive recovery stroke in normal pedaling); step-like loading (hip and knee extension while bike pedals backward through proximal pedal position, then hip and knee flexion through the distal position); and a “foot placement-like” task (alternating medial and lateral force) during normal pedaling. Also, tasks may be designed to target non-gait motions such as hip ab/adduction. The required task may be changed periodically, to incentivize attention to task and cortical control, rather than short-term adaptation (e.g. cerebellar).

A user display screen will indicate the desired task at all times, and indicate measures of asymmetry and performance. Performance will be defined as “task matching performance,” computed as the normalized projection of the vector-valued foot force or EMG signal (all channels) onto the specified task vector. Using this metric, 1.0 indicates perfect task matching; zero (0.0) indicates no force/EMG signal in the direction of the specified task; negative values indicate force production opposed to the specified task (impossible for EMG), and values greater than 1.0 indicate excess force or EMG activity in the specified pattern. We will also explore other methods for reducing multidimensional data to informative summary measures. Performance will be displayed to the user on a computer screen using a “speedometer” or similar graphical display, and will be incorporated into the control system of the robotic cycle and recorded for later analysis. Alternative measures of performance may also be used.

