***fMRI Scanning Protocol description:***

fMRI scans will be used to measure task-specific cortical activity in sensorimotor areas as outlined in the *data processing* section. Due to uncertainty about available testing equipment, one of two protocols may be used for fMRI testing: physical stepping with an MRI-compatible stepping machine (Ergospect GmbH; Forouzan et al., 2014), available at UW-Madison through [name]; or imagined/visualized cycling. The preferred activity is actual stepping with a passive MRI- compatible stepper. Imagined/visualized cycling is proposed as a suitable substitute activity within the constraints of the fMRI environment if for some reason the stepping machines cannot be used.

If the MRI-compatible equipment is available for this study, each subject will recline and position his head within the MRI bore, while his feet are clipped to the pedals. The torso will be stabilized with straps to minimize motion artifacts affecting the scan. During the scan, the subject will be instructed to step at a constant speed, while fMRI scans incrementally identify the activity in different portions of the brain. This protocol will best match the context of the fMRI scan to that of the training task.

If the MRI-compatible equipment is determined to be unsuitable for this study, each subject will recline and position his head within the MRI bore, with the body relaxed and stationary. During scanning, the subject will be instructed to imagine consistently performing the cycling task used in training. While not strictly equivalent to the real task, an imagined task (motor imagery) has been shown to evoke neural activity much as real tasks do (Pfurtscheller and Neuper, 1997; Porro et al., 1996; Sharma et al., 2006). Changes in such activity during imagined tasks will suggest that neural reorganization occurred.

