### **Aerobic Training Group (Control Group): Procedure**

Patients in the Control group will perform an identical protocol to that used by the Robotic group, except that the robotically-incentivized pedaling exercise will be replaced with an aerobic therapy program. This intervention will emulate an established form of motorized pedaling therapy similar to that used in commercial motorized exercise bikes to improve underlying cardiovascular unfitness contributions to gait impairment. This therapy implements a simple version of assist-as-needed and constant-velocity control. The patient's target pedaling speed (e.g. 20 rev/min (to be finalized through pilot tests: range 15-50 rev/min) and power level (set by heart rate to require approximately 50-70% of maximal oxygen uptake, estimated individually for each patient) are set at the beginning of each session and a motor provides assistance or resistance to compensate for the performance of the patient. The exercise will be performed in this mode for 30 minutes per training session.

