### **Healthy Normal Controls**

#### **Non-Stroke Group 1 (Typical Comparison Group): Procedure**

Healthy Normal subjects in this group will be administered the same behavioral measures as the Stroke groups, and 1 fMRI scan while stepping (or imagining stepping) at the beginning of the study. Subjects will then undergo up to 5 training sessions on the robotic cycle with a modified training task. This task will incentivize performance of a novel motor task, such as eccentric force control, mediolateral force control, or EMG coordination in a pattern different from normal cycling. Performance in matching the target task will be evaluated across the training sessions.

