***fMRI data:***

SPM5 (Wellcome Department of Cognitive Neurology, London, UK) will be employed for motion correction and used to normalize the EPI BOLD images to a standard space using a 12 parameter linear transformation. The images will be then spatially smoothed using an 8.0 mm Gaussian kernel. Finally, the statistical package contained within SPM5 will be used to estimate the effects of condition at each voxel according to the general linear model. The analysis will be entered into SPM5 as an epoch design of the fixed response/box car form convolved with canonical HRF, reflecting the appropriate activation and rest periods within the total scanning period. Images will be high-pass filtered at 128 s to remove low- frequency drifts in blood oxygen level-dependent signal.

Percent signal change (after vs. before) will be compared statistically between the two groups using unpaired two-sample t-tests between the robotic and aerobic groups. A repeated measures ANOVA will be performed with the dependent variable being the percent signal change and between subjects factor Group (robotic therapy, aerobic therapy), and within subject factor Time (before and after training).

Along with percent signal change over time, we will also compute region-wise laterality index. ROIs will be predefined in each hemisphere. For each ROI, laterality index (LI) will be defined as: Number of activated voxels in the affected hemisphere / [voxels in the left hemisphere + voxels in the right], thus giving LI for each ROI. LI = 0.5 indicates symmetrical activation; LI < 0.5 indicates an activation deficit on the affected side, and LI > 0.5 indicates increased activation of the affected side. This index will provide a way of

understanding the contribution of each brain area (ROI) to the overall task-related activation in one session and changes in laterality over time. The percent signal change and LI are purely quantitative measures, in order to ensure that change in plasticity over time is captured adequately and does not rely on individual fMRI reader's abilities to gauge these changes simply on the basis of a "visual read" of the fMRI scans.

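### If the imagery fallback is used, the scan task can differ by group, so the between-arm fMRI change may partly reflect what was imagined

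*Combined protocol and SAP*

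**What the plan says.** The fMRI Scanning Protocol description, placed under the Robotic Group procedure, gives two possible scan tasks. The preferred one is stepping at constant speed on an MRI-compatible stepper. If that equipment is unsuitable, the body stays still and "the subject will be instructed to imagine consistently performing the cycling task used in training". The same section takes changes in activity during imagery as a sign of neural reorganization.

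The Aerobic Training Group procedure gives controls the same protocol, "except that the robotically-incentivized pedaling exercise will be replaced with an aerobic therapy program". The robotic tasks mimic parts of gait, "including some which are not normally excited in typical cycling behavior". Of these tasks the plan adds: "The required task may be changed periodically, to incentivize attention to task and cortical control".

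Patients are scanned once before and once after the intervention. The fMRI data section states that percent signal change, after versus before, "will be compared statistically between the two groups using unpaired two-sample t-tests", and adds a Group by Time repeated measures ANOVA.

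The Typical Comparison Group has "1 fMRI scan while stepping (or imagining stepping) at the beginning of the study". The section on data from healthy normals makes the average map from these subjects the patients' control.

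Two places are less specific about what patients imagine. The Project Summary says: "All stroke patients will be scanned before and after their training program while performing or imagining simple motor tasks". The scanning section also names the fallback simply as imagined or visualized cycling.

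**The concern.** A between-arm comparison of brain activation is interpretable when both arms do the same thing in the scanner. The stepper task meets that condition. The fallback instruction points to whatever the patient trained on, and training is the one element that differs by arm. Followed as written, it makes the measurement task depend on the randomized group. Randomization balances patients; it does not balance a task that is assigned along with the treatment.

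At stake is the secondary objective, plasticity after robotic training compared with aerobic pedaling. A difference in signal change could be read as reorganization when part of it comes from imagining a different task. The healthy reference map has a related problem: it would come from imagined stepping while patients imagine cycling.

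**Working it through.** **1. The scan task by group, from the plan's text**

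| Group | Stepper available | Imagery fallback |
|---|---|---|
| Robotic | Constant-speed stepping | Task used in training: targeted force or EMG pedaling |
| Aerobic control | Constant-speed stepping | Task used in training: steady aerobic pedaling |
| Healthy comparison | Stepping | Imagined stepping |

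The first column is common to all groups. The second is not, if the operative instruction is followed literally. No section supplies an imagery script that would settle it.

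**2. When the difference matters for the planned test**

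Let c be the contribution of imagined content and familiarity to the measured signal. The between-arm difference in change then estimates

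(true plasticity difference) + [(c robotic, post − c robotic, pre) − (c control, post − c control, pre)].

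If c is the same at both scans within each arm, the bracket is zero and different imagery tasks do no harm to this test. The bracket need not be zero, for two reasons:

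- The first scan comes before training. The trained task is then unpractised, and the gain in familiarity by the second scan may differ between targeted pedaling and ordinary pedaling.
- The robotic task may be changed during training. If the imagery follows those changes, a patient's two scans use different imagined tasks. The plan does not say whether it would.

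**3. How many scans are involved**

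- Planned patient scans: 40 × 2 = 80.
- Completers, using the Sample Size section's 20% dropout: 20 × 0.80 = 16 per arm, which reproduces the plan's figure. That gives 32 patients and 32 × 2 = 64 scans in the change-score test.
- Healthy scans do not enter the between-arm test; they enter only the reference map.

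**4. Illustration of size (assumed shifts, not from the documents)**

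For one unpaired two-sided 5% t-test with 16 per arm, df = 30 and t(0.975) = 2.042. The smallest significant observed difference is 2.042 × √(2/16) = 0.722 SD of the change score. Suppose there is no true plasticity difference and the bracket in step 2 equals an assumed shift:

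| Assumed shift (SD) | Share of 0.722 SD | Probability that the test rejects |
|---|---|---|
| 0 | 0% | 0.05 |
| 0.25 | 35% | 0.105 |
| 0.5 | 69% | 0.278 |

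The rejection probabilities come from the noncentral t distribution with noncentrality shift × √(16/2). The table shows how sensitive a trial of this size would be to such a shift; it is no evidence that a shift exists. It applies to a single uncorrected test, such as one region of interest, and not to the cluster-corrected voxelwise analysis.

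**The case against.** Much of the opposing case is sound.

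- **It is conditional.** Stepping is preferred and the plan names a device available at the university. The fallback matters only if that device cannot be used, and then only for a secondary outcome in a pilot study. This stands.
- **A common task may be intended.** The Project Summary's wording and the generic name for the fallback both fit one task for all patients. At the first scan a patient has not yet met the targeted task, so ordinary cycling is the easier thing to imagine. This stands as a possible reading. However, neither phrase defines a task, and the only sentence that tells the subject what to do refers to training.
- **The arms' tasks overlap.** The robotic subject's explicit goal is to hold a constant speed, all tasks are seated pedaling, and emulating an exercise bike is a listed option. This stands, and it could make any content difference small.
- **Matching the scan to training is deliberate.** Changed activity during a practised task is arguably the plasticity being sought. This has force for a within-arm description. It has less force for the between-arm test, and the plan's own preferred task is already common to both arms.
- **Imagery may not follow changes in the robotic task.** Nothing says that it would, so this route to bias is only possible.

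A reader might go further and infer that the arms will certainly imagine different tasks, or that the fMRI comparison is invalid. The documents support neither inference: the wording is open, the fallback may never be used, and an effect that is constant within each arm cancels.

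**Conclusion.** The point holds in a limited form. If the imagery fallback is used, the stated instruction together with the control-arm procedure lets imagined content differ between arms, and possibly between a patient's two scans. The healthy group's imagery differs from the patients' as well. The between-arm change in percent signal could then partly reflect what was imagined. The analyses in the Behavioral Data section that use percent signal change, namely the multivariate ANOVA and the regression, would carry the same ambiguity. The gait outcomes would still be measured in the same way.

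Neither the size nor the direction of any bias can be found from the documents, and it may be zero. The conclusion rests on three assumptions: the fallback is used, the instruction is applied literally in each arm, and the content or familiarity effect changes differently between scans in the two arms. This is a cheap improvement worth making before any imagery scan is acquired, since scans taken under arm-specific imagery could not be corrected afterwards.

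**What to change.** In the fMRI Scanning Protocol description, replace the reference to the trained task with one fixed, cued imagery task. Use the same script in both arms, at both scans and in the healthy comparison group. Imagined stepping at constant speed is a natural choice, because it mirrors the preferred stepper task and agrees with the Typical Comparison Group procedure. If imagery of the trained task is wanted, keep it as a separate exploratory run outside the between-arm test.

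The cost is a one-sentence amendment and a short script, with no added subjects or scan sessions; an exploratory run would add some scan time. There are two downsides. A common task may be less sensitive to task-specific learning, which the stepper option already accepts. A common script also equalizes content but not all familiarity: if constant-speed stepping resembles one arm's training more than the other's, some differential familiarity may remain and should be acknowledged when the result is interpreted.

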***Summary of study visits/procedures: Robotic group***

Subjects assigned to the Robotic group will complete the following study visits. Note the timeline and schedule of visits given below is only representative; for example, conditions beyond the control of the study group and patient –related factors may lead to fewer number of visits per week and not all study events may be completed during one visit. We will seek to maintain a constant number of 12 training visits for all stroke subjects. Subjects who drop out before this number may be replaced at the discretion of the PI.

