***Study Procedure***

***Subject Assessments***

### ***Behavioral Assessment:***

The following commonly used measures of lower extremity motor assessment, standard stroke scales, and measures of activities of daily living will be administered at starting and ending time points to all patients over the length of the study. Healthy normal controls will complete these measures at the beginning of the study. Pilot controls (enrolled before other groups as well as throughout the study for continuing development) will complete a subset as deemed necessary for preparing the study and the study team for the patient and control groups. The assessments are as follows:

1. Six Minute Walk Test (6MWT): The 6MWT is a simple series of laps along a 30 m straight path in a level hallway. Subjects will be instructed to walk as far as they can in six minutes back and forth along this path, according to standard instructions (Rehab Measures - 6 Minute Walk Test). They will be allowed to use mobility aids, to stop or to rest as necessary. Total distance walked will be recorded based on the number of laps (including any fractional last lap), as well as from the IMU motion reconstruction.
2. Timed Up-and-Go test (TUG): The TUG is a simple timed test of how long it takes to stand up, walk 10 feet, turn around, return to the starting point, and sit down. Subjects will be instructed to perform this sequence as quickly as they safely can, using standard instructions (Podsiadlo and Richardson, 1991). The test will be performed in a laboratory or hallway setting.
3. Self-Selected Walking Speed (SSWS): A simple test of the speed a person chooses to walk over a 5-meter distance.
4. Fastest Comfortable Walking Speed (FCWS): A similar test of the “fastest comfortable speed” a person can use to walk over the 5-meter distance

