**Timeline:**

- **Timepoint 1 Visit** – will include baseline behavioral assessments, gait tests,

written questionnaires, and fMRI scan

- Training session #1 : [this could occur on the same day as the first behavioral and fMRI sessions]
- Visit 2 – training session #2
- Visit 3 – training session #3
- Visit 4 – training session #4
- Visit 5 – training session #5
- Visit 6 – training session #6
- Visit 7 – training session #7
- Visit 8 – training session #8
- Visit 9 – training session #9
- Visit 10 – training session #10
- Visit 11 – training session #11
- Visit 12 – training session #12
- **Timepoint 2 Visit** – will include endpoint behavioral assessments, gait tests, written questionnaires, and fMRI scan 2 at the end of the intervention . This visit could occur on the same day as the final intervention, or the next day or two per subject and experimenter convenience.–

Each behavioral session will take roughly 1 hour. Each intervention session will take about 1 hour. Each fMRI scan session will take 2 hours. The behavioral and fMRI sessions will take place at WIMR; the training sessions will take place at the UW-Madison Mechanical Engineering Building. We will arrange and pay for transportation between sites as needed.

Evidence suggests that targeted lower limb cycle training can improve walking distance and speed in stroke patients. Some example studies used a program of 10-15 training sessions over 2-3 weeks (Brown et al., 2005; Katz-Leurer et al., 2006), and 12 sessions over 4 weeks have been used in robotic gait training (Krishnan et al., 2013). This basis suggests that the intended duration and intensity of training (12 sessions of 30 minutes over 4 weeks) will be sufficient to demonstrate improvements in gait and motor function if they occur. However, this protocol is a target, which may be adjusted for individual patients as necessary to accommodate schedules and other needs. In such cases, the goal will be to keep the total number of training sessions constant for all patients. However, if interim results [after 6-10 patients] suggest that 12 sessions is not sufficient, then the study team will make provisions to increase the number of study sessions. Finally, if it appears that the subject will take more than 15 sessions to complete the study, then subject participation in the study will end.

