### **Subject randomization:**

Subjects with stroke will be randomly assigned to the intervention [robotic] or non-intervention [aerobic/control group]. Randomization will be done using a block design. We will control for sex (male vs female) and stroke severity (based on Fugl Meyer assessment) to ensure comparability across groups.

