### **Sample Size**

Below we give sample size calculations based on the gait outcome measures (six-minute walk test (6MWT), self-selected walking speed (SSWS) and fastest comfortable walking speed (FCWS)), as well as the expected changes in brain activations:

The sample size required per group is computed using the following formula:  $N$  (per group) =  $2 * ( (z(1-\alpha/2) + z(\beta)) * \sigma / d )^2$ , where  $d$  is the expected difference in outcome value, post- vs. pre-training;  $\sigma$  is the estimated standard deviation;  $\alpha$  is the alpha error we would like to control; and  $\beta$  is the statistical power. Here we set a statistical goal of 80% power ( $\beta = 0.80$ ,  $z(\beta) = 0.84$ ) and  $\alpha$  level 0.05 ( $z(1 - \alpha/2) = 1.96$ ).

Based on a recent study of locomotor rehabilitation in chronic stroke (Bowden et al., 2013), we expect: a difference in 6MWT of 154.3 +/- 171.1 meters; a difference in SSWS of 0.21 +/- 0.13 m/s; and a difference in FCWS of 0.18 +/- 0.15 m/s. These give sample size estimates of 20, 6 and 11 subjects, respectively. This sample-size estimate is conservative, using a two-tailed test when in fact we expect to test explicitly for an

increase (one-tailed test). For a one-tailed distribution (using  $z(1 - \alpha) = 1.65$ ), sample size estimates are 16, 5 and 9 subjects.

For fMRI signal changes at the single voxel level, we expect to achieve statistical power of 80% with a significance cutoff of alpha = 0.05 using a sample size of 12 subjects, as reported in literature (Desmond and Glover, 2002).

The maximum of all sample size estimates for two-tailed tests is 20 subjects. However, the outlier is the 6MWT; without this, the maximum would be 12 subjects. Balancing the practical (budgetary, time) need for a small sample with the need to capture as many metrics as possible, **we choose a sample size of 16**. This sample size just captures the expected change in 6MWT (in a one-tailed test) and is well above the necessary sample size for other outcomes. Based on previous experience, we estimate a 20% dropout rate (due to patients not being able to complete all sessions, or not coming back for post training evaluation). We therefore propose to enroll 20 patients per group (robotic, aerobic), for a total of 40 patients.

Up to 20 healthy controls will be enrolled to form a normal data set of similar size to each patient group.

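### Patients who stop before 12 sessions may be replaced at the PI's discretion, and nothing says they are still assessed or analysed as randomised, so the pre/post comparison is likely to become completers-only

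*Combined protocol and SAP*

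**What the plan says.** All references are to the combined protocol and SAP.

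- **Replacement** (Summary of study visits/procedures: Robotic group). The aim is 12 training visits for every stroke patient. "Subjects who drop out before this number may be replaced at the discretion of the PI". The Aerobic Training Group section gives the control arm the same protocol apart from the exercise, so this applies to both arms.
- **Assessments** (Behavioral Assessment; Functional MRI scans). The behavioral and gait measures "will be administered at starting and ending time points to all patients over the length of the study". The scanning section likewise gives all patients a scan before and after.
- **Timing of the post visit** (Timeline). Timepoint 2 "will include endpoint behavioral assessments, gait tests, written questionnaires, and fMRI scan 2 at the end of the intervention", on the day of the last session or a day or two later. The same section says that "if it appears that the subject will take more than 15 sessions to complete the study, then subject participation in the study will end".
- **Dropout** (Sample Size). "we estimate a 20% dropout rate (due to patients not being able to complete all sessions, or not coming back for post training evaluation". Non-completion is listed separately from failure to return. Then: "We therefore propose to enroll 20 patients per group (robotic, aerobic), for a total of 40 patients".
- **Allocation** (Subject randomization). "Randomization will be done using a block design", controlling for sex and Fugl-Meyer severity. Added patients are not mentioned.
- **Analysis** (Data Processing/Data Analysis). ANOVA and multivariate ANOVA with pre/post time as a within-subject factor and group between subjects, plus t-tests on the fMRI change. No analysis population, no rule for missing post values and no treatment of replaced patients is given.

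**The concern.** Taken together, these rules lead a patient who stops early out of the comparison. The post visit hangs on finishing, non-completion counts as dropout, and the place may be given to someone else. A pre/post analysis needs both values, so a patient without Timepoint 2 contributes nothing to it unless the plan provides otherwise.

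At stake is the randomised comparison. If early stoppers would have gained less than completers, leaving them out flatters an arm in proportion to how many stop and how far they differ. This cancels when both arms lose patients in the same way and does not cancel otherwise. Adding a new patient restores the count but does not bring back the missing outcome, so it does not remove any shift. The terms of replacement are also open: there is no trigger, no maximum, no link to the randomisation section, and no statement that the replaced patient's data are kept.

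**Working it through.** **The plan's own figures.** Inputs from Sample Size: 6MWT difference 154.3 m, SD 171.1 m, z = 1.65 (one-tailed) or 1.96 (two-tailed), z = 0.84 for 80% power.

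- One-tailed: 2 × ((1.65 + 0.84) × 171.1 / 154.3)² = 15.2, rounded up to 16 per arm.
- Two-tailed: 2 × ((1.96 + 0.84) × 171.1 / 154.3)² = 19.3, rounded up to 20 per arm.
- Dropout allowance: 16 / (1 − 0.20) = 20 per arm, 40 in total.

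The stated 16 and 20 reproduce. The 20% allowance is already in the 40. Expected dropouts are 0.20 × 40 = 8, or 4 per arm.

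**Size of a completers-only shift.** Let a fraction f of an arm leave, and let leavers' 6MWT gain be k SD worse than completers'. The completers' mean exceeds the all-randomised mean by f × k × SD. The shift in the arm difference is (f₁k₁ − f₂k₂) × SD. The documents give f = 0.20 overall and the SD. The values of k and any difference between arms are assumptions.

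| Assumed scenario | Shift in 6MWT difference |
|---|---|
| 20% leave each arm; gap of 0.5 SD in one arm only | 0.20 × 0.5 × 171.1 = 17.1 m |
| 20% leave each arm; gap of 1 SD in one arm only | 0.20 × 1.0 × 171.1 = 34.2 m |
| 30% vs 10% leave; gap of 0.5 SD in both arms | (0.30 − 0.10) × 0.5 × 171.1 = 17.1 m |
| 30% vs 10% leave; gap of 1 SD in both arms | (0.30 − 0.10) × 1.0 × 171.1 = 34.2 m |
| Same rate and same gap in both arms | 0 m |

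The 1 SD case is extreme. If completers gain the planned 154.3 m, leavers would change by 154.3 − 171.1 = −16.8 m, that is, get worse.

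**Against precision.** At 16 per arm the standard error is 171.1 × √(2/16) = 60.5 m. With t on 30 degrees of freedom (2.04) the 95% half-width is about 124 m. The illustrated shifts are 17.1/124 = 14% and 34.2/124 = 28% of it.

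**What calling patients back would gain.** Suppose 2 of the 4 stoppers per arm return and represent all 4. Stoppers are then 2/18 of the observed patients instead of 4/20. In the one-arm scenario the shift falls to (0.20 − 2/18) × 0.5 × 171.1 = 7.6 m, or 15.2 m at 1 SD.

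**What a model using all baselines would gain.** Take the 17.1 m case with an assumed baseline–change correlation of −0.3. If leaving depends on baseline, the adjustment removes the shift. If leaving depends on the change itself, about (1 − 0.3²) × 17.1 = 15.6 m remains. If leaving is unrelated to baseline, all 17.1 m remains.

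**Whether adding patients is reasonable.** With 20 per arm and true dropout of 20%, the binomial chance of more than 4 dropouts, hence fewer than 16 completers, is 0.370 in one arm. For at least one of the two arms it is 1 − 0.630² = 0.60.

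**The case against.** The strongest reply is that the assessment and scanning sections already cover all patients. Read literally that includes early stoppers, and the replacement sentence speaks of dropping out, which could mean leaving the study and not merely stopping training. The Sample Size wording is a planning allowance, not a rule that excludes data. This is fair, and it is why the point is that the plan leaves the matter open and leans towards completers, not that it excludes early stoppers. A reader might infer that exclusion is prescribed; no section says so.

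Three other stronger readings are tempting.

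- That the PI could use the continuous review of fMRI and EMG data to choose whom to replace. The documents show no route from that review to a biased gait result. A replacement is a new patient with an unknown outcome, and someone who leaves early would normally have no Timepoint 2 value when the decision is made.
- That 48 patients will be randomised. This follows only if all 8 expected dropouts are replaced and the 40 is not itself a count after replacement. The text says only that replacement may happen.
- That replacement is improper in itself. The 37% and 60% figures argue for permitting added patients. What is missing is written terms.

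It also stands that the shift is an assumed scenario, that no section gives evidence of different stopping by arm, and that it is small beside the sampling error of a pilot of this size.

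**Conclusion.** The concern holds in a limited form. Discretionary replacement, a post visit tied to finishing, and a dropout definition that includes non-completion, with no as-randomised analysis set, make a completers-only comparison likely. Whether a patient whose participation ends under the 15-session rule still has Timepoint 2 is also unclear; some may already have had 12 sessions.

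The resulting bias is conditional. It needs stopping rates that differ by arm, or a relation between stopping and outcome that differs by arm. The 17 to 34 m range rests on the plan's 20% rate and 171.1 m SD together with an assumed gap of 0.5 to 1 SD confined to one arm. It does not by itself undermine the trial, but it is an avoidable weakness in the randomised comparison and cheap to close. It is an improvement that should be made, not a fatal flaw.

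**What to change.** 1. State that the before and after assessments apply to every randomised patient whatever the number of sessions completed. Seek the Timepoint 2 gait tests, and the scan where feasible, from those who stop early or whose participation in training ends under the 15-session rule, subject to consent. This concerns outcome collection only and leaves the rule for ending training as it is.
2. Make the main analysis all randomised patients with available data, in the assigned arm, preferably with a baseline-adjusted or likelihood model that uses all baselines. Such a model deals with leaving that depends on observed baseline but not with leaving that depends on the unobserved change, so it supports item 1 and does not replace it. Give completers as a sensitivity analysis, and report numbers and reasons for stopping by arm.
3. Either rely on the 20% allowance already in the sample size, or state in advance the trigger and maximum for added patients, reconciled with the 40. In the second case, say that each is newly randomised under the randomisation section and that the replaced patient's data are kept.

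Cost: protocol wording and up to about 8 return visits of a type already planned. By the Timeline durations (1 hour behavioral, 2 hours fMRI) that is 8 × 1 = 8 hours, or 8 × 3 = 24 hours with scans, plus payment and transport. Consent or IRB wording may need to change; the consent pages were not available to check. Some patients will still not return, and if no one is added an arm may end below 16 completers.
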